## **7 DOSING DELAYS/DOSE MODIFICATIONS.**

### **Telaglenastat (CB-839) HCl**

Based on available data, AEs that are most likely to be observed with Telaglenastat (CB-839) HCl treatment include fatigue, GI events (nausea, vomiting, anorexia), photophobia, and elevated LFTs. Careful application of the dose-escalating rules and close observation of the subjects should minimize the potential risk of dosing with Telaglenastat (CB-839) HCl. The study personnel must be able to recognize and diagnose these potential AEs and initiate prompt intervention. In general, grade 1 events should be managed with appropriate supportive care, dosing can be interrupted for persistent drug-related grade 2 events, and the dose should be reduced for most Telaglenastat (CB-839) HCl-related grade 3/4 toxicities. In particular, regular monitoring of LFTs is recommended. Grade  $>2$  elevations in ALT or total bilirubin should lead to an interruption of study drug and grade  $\geq 3$  events should lead to dose reduction upon restarting Telaglenastat (CB-839) HCl.

Blood Bilirubin Increase	Management/Next Dose for Telaglenastat (CB-839) HCl	Management/Next Dose for Osimertinib (AZD9291)
Grade 1	No change in dose.	No change in dose
Grade 2	Hold until $\leq$ grade 1. Resume at same dose level.	Hold until $\leq$ grade 1. Resume at same dose level.
Grade 3	Hold* until $\leq$ grade 1. Resume at one dose level lower, if indicated. **	Hold* until $\leq$ grade 1. Resume at one dose level lower, if indicated. **
Grade 4	Hold* until $\leq$ grade 1. Resume at one dose level lower, if indicated. **	Hold* until $\leq$ grade 1. Resume at one dose level lower, if indicated. **

\*Patients requiring a delay of  $>2$  weeks should go off protocol therapy.

\*\*Patients requiring  $> 2$  dose reductions of Telaglenastat (CB-839) HCl or  $> 1$  dose reduction in Osimertinib (AZD9291) must go off protocol therapy.

Alanine Aminotransferase Increased	Management/Next Dose for Telaglenastat (CB-839) HCl	Management/Next Dose for Osimertinib (AZD9291)
Grade 1	No change in dose.	No change in dose
Grade 2	Hold until $\leq$ grade 1. Resume at same dose level.	Hold until $\leq$ grade 1. Resume at same dose level.
Grade 3	Hold* until $\leq$ grade 1. Resume at one dose level lower, if indicated. **	Hold* until $\leq$ grade 1. Resume at one dose level lower, if indicated. **
Grade 4	Hold* until $\leq$ grade 1. Resume at one dose level lower, if indicated. **	Hold* until $\leq$ grade 1. Resume at one dose level lower, if indicated. **

\*Patients requiring a delay of  $>2$  weeks should go off protocol therapy.

Alanine Aminotransferase Increased	Management/Next Dose for Telaglenastat (CB-839) HCl	Management/Next Dose for Osimertinib (AZD9291)
** Patients requiring $> 2$ dose reductions of Telaglenastat (CB-839) HCl or $> 1$ dose reduction in Osimertinib (AZD9291) must go off protocol therapy.		

Other AEs	Management/Next Dose for Telaglenastat (CB-839) HCl	Management/Next Dose for Osimertinib (AZD9291)***
Grade 1	No change in dose. Administer standard supportive care.	No change in dose
Grade 2	For persistent grade 2 toxicity****: Hold until $\leq$ grade 1. Resume at same dose level.	For persistent grade 2 toxicity****: Hold until $\leq$ grade 1. Resume at same dose level.
Grade 3	Reduce dose by one level if event is related to Telaglenastat (CB-839) HCl.*	Hold* until $\leq$ grade 1. Resume at one dose level lower, if indicated. **

Grade 4	Reduce dose by one level if event is related to Telaglenastat (CB-839) HCl.*	Hold* until $\leq$ grade 1. Resume at one dose level lower, if indicated.**
---------	--	---

\*Patients requiring a delay of  $>2$  weeks should go off protocol therapy.

\*\* Patients requiring  $> 2$  dose reductions of Telaglenastat (CB-839) HCl or  $> 1$  dose reduction in Osimertinib (AZD9291) must go off protocol therapy.

\*\*\* Osimertinib (AZD9291) must be permanently discontinued for ILD/pneumonitis or QTc interval prolongation with signs/symptoms of serious arrhythmia

\*\*\*\* Persistent grade 2 toxicities include those that do not resolve within 7 days despite optimal

supportive care or result in treatment delay  $> 14$  days

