## **6.4 Duration of Therapy**

NCI Protocol #: 10216

Version Date: 09/17/2024

In the absence of treatment delays due to AE(s), treatment may continue until one of the following criteria applies:

- Disease progression
- Intercurrent illness that prevents further administration of treatment
- Unacceptable AE(s)
- Patient decides to withdraw from the study
- General or specific changes in the patient's condition render the patient unacceptable for further treatment in the judgment of the investigator
- Clinical progression
- Patient non-compliance
- Pregnancy
  - All women of child bearing potential should be instructed to contact the investigator immediately if they suspect they might be pregnant (e.g., missed or late menstrual period) at any time during study participation.
  - The investigator must immediately notify CTEP in the event of a confirmed pregnancy in a patient participating in the study.
- Termination of the study by sponsor
- The drug manufacturer can no longer provide the study agent

The reason(s) for protocol therapy discontinuation, the reason(s) for study removal, and the corresponding dates must be documented in the CRF.

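### Section 7 sets hold rules for ALT and bilirubin but not AST, so an AST-led rise requires no telaglenastat hold at non-persistent grade 2 or at grade 3-4

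*Combined protocol and SAP*

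**What the plan says.** The opening text of Section 7 (Telaglenastat) states that "elevations in ALT or total bilirubin should lead to an interruption of study drug"; the threshold printed before these words is grade >2. The sentence goes on to say that grade 3 or higher "events should lead to dose reduction upon restarting Telaglenastat (CB-839) HCl". For toxicity in general, "dosing can be interrupted for persistent drug-related grade 2 events".

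Three tables follow: blood bilirubin, ALT, and *Other AEs*. The bilirubin and ALT tables hold both drugs to grade 1 or lower at grades 2, 3 and 4, whatever the cause or duration. After a grade 3 or 4 hold they say "Resume at one dose level lower, if indicated".

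The *Other AEs* table holds at grade 2 only when the toxicity is persistent. Its footnote says: "Persistent grade 2 toxicities include those that do not resolve within 7 days despite optimal" supportive care, or those that delay treatment by more than 14 days. At grades 3 and 4 the telaglenastat cell reads "Reduce dose by one level if event is related to Telaglenastat (CB-839) HCl". An asterisk there points to the rule that patients needing a delay of more than 2 "weeks should go off protocol therapy". The osimertinib cell in the same rows does order a hold.

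No table, footnote or sentence in Section 7 mentions AST.

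**The concern.** AST and ALT are handled as a pair almost everywhere else: in eligibility (Section 3.1.9), hepatitis B monitoring (3.4.4), the telaglenastat risk list (10.1.1.1), the calendar's liver trigger (11.1, footnote c) and the Hy's Law definitions (Appendix E). Only the dose-modification rules separate them, and no reason is given.

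For an AST-led rise, a site following the tables may therefore keep giving telaglenastat where an ALT rise of the same grade would have stopped it. The result also runs the wrong way between the two drugs. The telaglenastat risk list names AST increase as possibly related. The osimertinib list (10.1.1.2) puts AST among events with insufficient evidence of causation. Yet at grade 3-4 the *Other AEs* table holds osimertinib and does not require a hold of telaglenastat. What is at stake is the safety of individual patients still on telaglenastat, not an endpoint of the trial.

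**Working it through.** **Step 1: required telaglenastat action, by grade.** AST is read under *Other AEs*, the only table that can apply to it.

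| Grade | ALT table | AST, under *Other AEs* |
|---|---|---|
| 1 | No change | No change, supportive care |
| 2, not persistent | Hold to grade 1 or lower | No hold required |
| 2, persistent | Hold to grade 1 or lower | Hold to grade 1 or lower |
| 3 | Hold to grade 1 or lower; lower dose if indicated | One level down if related; no hold, no recovery grade |
| 4 | As grade 3 | As grade 3 |

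The rules differ at non-persistent grade 2 and at grades 3-4. For osimertinib they differ only at non-persistent grade 2. If a grade 3-4 AST rise is judged unrelated to telaglenastat, the table requires no change to that drug. The 2-week asterisk allows for a delay but does not order one.

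**Step 2: does another section close the gap?** Calendar footnote c sends AST of 3 x ULN or more to Appendix E. That appendix covers identification and reporting of Hy's Law cases, orders no hold, and refers management back to Section 7. The DLT definition (6.2) orders no hold. Section 3.4.4 asks only that interruption or discontinuation be considered, and only on hepatitis B reactivation. The gap stays open.

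**Step 3: rough size at grade 3.** The only rate given is 2.3% with grade 3 LFTs among 88 patients on the twice-daily schedule of a monotherapy study (Section 2.2.1.3.2). It covers any liver test.
- Count: 0.023 x 88 = 2.02, so 2/88 = 2.27%; exact (Clopper-Pearson) 95% CI 0.28% to 7.97%.
- The number still on telaglenastat is not stated. Assume k = 1, 5 or 10, where 10 is the planned expansion cohort.
- Expected events = k x 0.0227: 0.02, 0.11, 0.23.
- Chance of at least one = 1 - (1 - 0.0227)^k: 2.3%, 10.9%, 20.5%.
- For k = 10 at the CI limits: 0.03 to 0.80 events, and a 2.7% to 56.4% chance of at least one.

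AST-led cases are a subset of these. The rate is for the monotherapy study as a whole, whereas at most 164 days remained from this version (09/17/2024) to 2/28/2025.

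**Step 4: rough size at grade 2.** No grade 2 AST rate is given. The telaglenastat risk list (161 patients, the monotherapy count in Section 2.2.1.3) puts related AST increase at 20% or less, with no split by grade. If 20% applied, the expected count in 10 patients is 0.20 x 10 = 2.0. That is not a maximum: at a 20% rate the chance of 3 or more in 10 is 1 - 0.678 = 32%.

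**Step 5: serious events.** Two patients had related serious AST and/or ALT increases, out of 161 + 94 = 255 treated: 2/255 = 0.8%. How many were AST-led is not stated.

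**The case against.** The strongest case is that this is at most a wording clarification. AST is watched: it is in every chemistry panel, a value of 3 x ULN triggers prompt review under Appendix E, and Section 7 asks for prompt intervention on elevated LFTs. Investigators may interrupt or stop treatment (Sections 6.4 and 7). No document reports an AST-led rise. The missing grade 3-4 hold is not peculiar to AST, since it applies to every event outside ALT and bilirubin. On dose reduction, *Other AEs* is firmer for related events than the ALT table's conditional wording.

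All of this stands and limits the priority. None of it supplies the missing instruction: review and discretion are not a required hold, and AST's paired enzyme has one.

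Some stronger readings are tempting but unsupported:
- *That telaglenastat runs on at full dose through severe AST rises.* A related grade 3-4 event requires a one-level reduction.
- *That DLT counts or the RP2D are affected.* Section 6.2 does not depend on which enzyme is raised.
- *That 22 patients (12 escalation plus 10 expansion) are exposed.* Four of the 12 had progression as best response (Section 2.3), and progression ends treatment.
- *That the printed grade >2 is a deliberate third threshold.* The same sentence then uses grade 3 or higher for reduction, so >2 may be a slip for 2 or higher, which would match the tables.

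**Conclusion.** The point holds as a low-priority safety inconsistency. Followed literally, Section 7 lets telaglenastat continue through a non-persistent grade 2 AST rise. It also lets the drug continue through a grade 3-4 rise, one level lower if related and unchanged if not, where the same ALT grade must be held. It affects isolated or AST-led rises only.

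The size is small and imprecise. With an assumed 10 patients on drug, about 0.23 grade 3 liver-test rises of any kind would be expected. That figure borrows a monotherapy rate for a combination and cannot isolate AST. Accrual is closed and telaglenastat supply ends on 2/28/25, which bounds the exposure further.

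**What to change.** Three edits in Section 7:

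1. Retitle the ALT table *ALT or AST increased (use the higher grade)*.
2. Set its grade 3-4 telaglenastat cells to: *hold until grade 1 or lower, or baseline; restart one level down if related to telaglenastat*. This keeps in the table itself the firmer reduction rule that AST has now. The baseline clause matters because Section 3.1.9 admits patients with liver metastases at AST up to 5 x ULN. It should also go into the grade 2 row and the osimertinib cells, so that both drugs restart on the same criterion.
3. In the interruption sentence, name AST beside ALT and bilirubin and set the threshold at grade 2 or higher, matching the tables. Make the reduction clause that follows agree with the revised cells.

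No new test is needed. The cost is occasional extra holds of both drugs for grade 2 AST rises, some of them non-hepatic. The expected count is up to about 2 in 10 if the 20% limit for related monotherapy events applied. Holds regardless of cause could exceed that. A grade 3-4 AST hold lasting more than 2 weeks would also take a patient off protocol therapy. Closed accrual is no bar: the sponsor refused only eligibility changes on that ground, and the same amendment added toxic epidermal necrolysis to Section 7.

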## 6 TREATMENT PLAN

### 6.1 Agent Administration

Treatment will be administered on an outpatient basis. Reported AEs and potential risks are described in Section 10. Appropriate dose modifications are described in Section 7. No investigational or commercial agents or therapies other than those described below may be administered with the intent to treat the patient's malignancy.

**Dose Escalation Treatment Plan:** A single arm dose escalation portion of the study will first be performed to determine the optimal dosing strategy where three dose levels will be assessed. Extensive PK studies will also be conducted to assess for any potential drug-drug interactions through the obtaining of peripheral blood. Eligible patients will initially receive treatment with single agent Telaglenastat (CB-839) HCl BID according to the dose escalation strategy and PK sampling will be done on Day 15. Starting on Day 16, patients will then go on to receive both Osimertinib (AZD9291) 80 mg PO QD as well as Telaglenastat (CB-839) HCl PO BID at the same dose as initially provided during the monotherapy portion of the study and a second set of PK analyses will be conducted on Day 1 of Cycle 2 for both Osimertinib (AZD9291) and Telaglenastat (CB-839) HCl (see table below). Peripheral blood will also be obtained for a PK assessment at the beginning of each 28- day treatment cycle starting with Cycle 2. An assessment for response to treatment will be conducted with a CT of the chest, abdomen, and pelvis (C/A/P) every 2 months as is standard practice.

Patients will continue to receive treatment until the time of disease progression, unacceptable toxicity, or treatment is discontinued based on patient/physician preference.

Patients enrolled to the dose escalation portion of the study will be treated according to a dose escalation schedule where three different dose levels will be assessed. For all dose levels, the Osimertinib (AZD9291) dose will be set at 80 mg PO QD. The dose levels of Telaglenastat (CB-839) HCl are as follows:

1) 400 mg PO BID; 2) 600 mg PO BID; 3) 800 mg PO BID. Dose Level -1 will be 200 mg Telaglenastat (CB- 839) HCl BID.

Phase 1 Dose Escalation Schedule		
Dose Level	Dose*	
	Telaglenastat (CB-839) HCl (mg) orally BID	Osimertinib (AZD9291) (mg) orally daily
Level -1	200 mg	80 mg
Level 1 (Starting Dose)	400 mg	80 mg
Level 2	600 mg	80 mg
Level 3	800 mg	80 mg

BID = twice daily, QD = once daily  
\*Dosing is given orally on a continuous schedule

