### Osimertinib (AZD9291)

#### **Dose Adjustments for Osimertinib (AZD9291):**

Dose Level	Osimertinib (AZD9291) Dose (QD)
Starting Dose	80 mg
Dose Reduction	40 mg

All patients in the phase 2 study will commence treatment with Osimertinib (AZD9291) at 80 mg daily. If a patient experiences a persistent drug-related grade 2 event or any CTCAE grade 3 or higher and/or unacceptable toxicity (any grade), where the clinician considers the event of concern to be specifically associated with Osimertinib (AZD9291) (and not attributable to the disease or disease-related processes for which patient is being treated), dosing will be interrupted, and supportive therapy administered as required in accordance with local practice/guidelines. If a toxicity resolves or reverts to  $\leq$ CTCAE grade 2 within 3 weeks of onset, treatment with Osimertinib (AZD9291) may be restarted at the same dose (80 mg) or a lower dose (40 mg) using the rules indicated in the above table for dose modifications and with discussion and agreement with the Sponsor Study Team Physician as needed. There will be no individual modifications to dosing schedule in response to toxicity, only potential dose reduction or dose interruption. If the toxicity does not resolve to  $\leq$ CTCAE grade 2 after 3 weeks, then the patient should be withdrawn from the study and observed until resolution of the toxicity.

Dose adjustment for AEs should be in accordance with the following table:

Dose Adjustment Information for Adverse Reactions		
Target Organ	Adverse Reaction	Dose Modification

Pulmonary	ILD/Pneumonitis	Permanently discontinue Osimertinib (AZD9291)
Cardiac	QTc interval greater than 500 msec on at least 2 separate ECGs	Withhold Osimertinib (AZD9291) until QTc interval is less than 481 msec or recovery to baseline if baseline QTc is greater than or equal to 481 msec, then restart at a reduced dose (40 mg) or at 80 mg (at the discretion of the investigator, to allow for situations where
		causality in relation to osimertinib may be difficult to determine).
	QTc interval prolongation with signs/symptoms of serious arrhythmia	Permanently discontinue Osimertinib (AZD9291)
Other	Grade 3 or higher adverse reaction	Withhold Osimertinib (AZD9291) for up to 3 weeks
	If grade 3 or higher adverse reaction improves to grade 0-2 after withholding of Osimertinib (AZD9291) for up to 3 weeks	Osimertinib (AZD9291) may be restarted at the same dose (80 mg) or a lower dose (40 mg)

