### **Interstitial Lung Disease (ILD)/Pneumonitis-like toxicity:**

If new or worsening pulmonary symptoms (e.g., dyspnea) or radiological abnormality suggestive of interstitial lung disease is observed, an interruption in study treatment dosing is recommended, and the AstraZeneca study team should be informed. It is strongly recommended to perform a full diagnostic workup, to exclude alternative causes such as lymphangitic carcinomatosis,

infection, allergy, cardiogenic edema or pulmonary hemorrhage. The results of full diagnostic workup (including high resolution computed tomography (HRCT), blood and sputum culture, hematological parameters) will be captured by eCRF. In the presence of confirmatory HRCT scans where other causes of respiratory symptoms have been excluded, a diagnosis of interstitial lung disease should be considered and study treatment permanently discontinued

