#### 10.1.1 CAEPRs for CTEP IND Agents

##### 10.1.1.1 CAEPR for Telaglenastat (CB-839) HCl

Below is the CAEPR for Telaglenastat (CB-839) HCl. Frequency is based on 161 patients.

Version 2.2, July 21, 2019

Adverse Events with Possible Relationship to Telaglenastat (CB-839) HCl (CTCAE 5.0 Term) [n= 161]			Specific Protocol Exceptions to Expedited Reporting (SPEER)
Likely (>20%)	Less Likely (<=20%)	Rare but Serious (<3%)	
BLOOD AND LYMPHATIC SYSTEM DISORDERS			
	Anemia		
EYE DISORDERS			
	Photophobia		
GASTROINTESTINAL DISORDERS			
	Nausea		Nausea (Gr 2)
	Vomiting		
GENERAL DISORDERS AND ADMINISTRATION SITE CONDITIONS			
Fatigue			Fatigue (Gr 2)
INVESTIGATIONS			
	Alanine aminotransferase increased		Alanine aminotransferase increased (Gr 2)
	Alkaline phosphatase increased		
	Aspartate aminotransferase increased		Aspartate aminotransferase increased (Gr 2)
	GGT increased		
	Platelet count decreased		
METABOLISM AND NUTRITION DISORDERS			
	Anorexia		

This table will be updated as the toxicity profile of the agent is revised. Updates will be distributed to all Principal Investigators at the time of revision. The current version can be obtained by contacting [[contact]](mailto:[contact]). Your name, the name of the investigator, the protocol and the agent should be included in the e-mail.

Adverse events reported on Telaglenastat (CB-839) HCl trials, but for which there is insufficient evidence to suggest that there was a reasonable possibility that Telaglenastat (CB-839) HCl caused the adverse event:

**CARDIAC DISORDERS** - Sinus tachycardia

**GASTROINTESTINAL DISORDERS** - Constipation; Mucositis oral; Oral pain

**GENERAL DISORDERS AND ADMINISTRATION SITE CONDITIONS** - Death NOS; Fever

**INFECTIONS AND INFESTATIONS** - Hepatitis viral; Meningitis

**INVESTIGATIONS** - Blood bilirubin increased; Creatinine increased; Lymphocyte count decreased; Neutrophil count decreased

NCI Protocol #: 10216

Version Date: 09/17/2024

**METABOLISM AND NUTRITION DISORDERS** - Hyperglycemia; Hyponatremia; Hypophosphatemia

**MUSCULOSKELETAL AND CONNECTIVE TISSUE DISORDERS** - Arthralgia; Myositis

**NERVOUS SYSTEM DISORDERS** - Seizure

**RESPIRATORY, THORACIC AND MEDIASTINAL DISORDERS** - Dyspnea; Hypoxia

**SKIN AND SUBCUTANEOUS TISSUE DISORDERS** - Rash maculo-papular

**VASCULAR DISORDERS** - Hypertension; Hypotension

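### Section 7, 'Other AEs' table: telaglenastat-related grade 3 and 4 events call only for a one-level reduction, with no hold or recovery grade

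*Combined protocol and SAP*

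**What the plan says.** Section 7 has three dose-modification tables: blood bilirubin, ALT, and other adverse events. Each has a telaglenastat column and an osimertinib column.

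- **Other AEs, telaglenastat, grade 3 and grade 4 (same wording in both):** "Reduce dose by one level if event is related to Telaglenastat (CB-839) HCl". A single asterisk follows, whose footnote takes patients off protocol therapy if they need a delay of more than 2 weeks. The double asterisk, whose footnote caps telaglenastat at two reductions, is absent.
- **Other AEs, telaglenastat, grade 2:** "For persistent grade 2 toxicity: Hold until" grade 1 or less, then resume at the same dose. Persistent means unresolved within 7 days despite optimal supportive care, or causing a delay of more than 14 days.
- **Other AEs, osimertinib, grade 3 and 4:** hold until grade 1 or less, then resume one level lower if indicated. Both footnotes are attached.
- **Bilirubin and ALT, both drugs, grade 3 and 4:** the same hold.
- **Introductory text of Section 7:** "the dose should be reduced for most Telaglenastat (CB-839) HCl-related grade 3/4 toxicities". Above grade 2 it names an interruption only for ALT and total bilirubin.

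The same introduction says the events most likely with telaglenastat "include fatigue, GI events (nausea, vomiting, anorexia), photophobia, and elevated LFTs".

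**The concern.** A site that follows the two cells as written lowers telaglenastat by one level and keeps dosing while a related grade 3 or grade 4 event is still present. The footnote limits how long a delay may last, but nothing orders the delay or says when to restart. An investigator may still hold on clinical judgment, without a protocol trigger or restart grade.

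The cells are a catch-all for most of the drug's recognised toxicity. They would govern an isolated grade 3 AST rise, for example, while a grade 3 ALT rise is held. Appendix E does not close that gap: it disclaims being a full guide to managing liver tests and points back to Section 7.

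Such events have occurred. The dose rationale in Section 2.3 reports, among the 12 escalation patients, grade 3 fatigue possibly related to both agents (and likely to disease) and grade 3 failure to thrive possibly related to telaglenastat (and definitely to disease). Neither has its own table.

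**Working it through.** The plan gives no figure to reproduce. The check is a count of cells, a search for any other rule that would supply the hold, and simple dose and date arithmetic.

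**1. Grade 3/4 cells in Section 7.** 3 tables × 2 drugs × 2 grades = 12.

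| Table | Telaglenastat, grades 3 and 4 | Osimertinib, grades 3 and 4 |
|---|---|---|
| Bilirubin | hold (2 cells) | hold (2 cells) |
| ALT | hold (2 cells) | hold (2 cells) |
| Other AEs | reduce only (2 cells) | hold (2 cells) |

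With a hold: 4 + 4 + 2 = 10. Without: 12 − 10 = 2.

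**2. Does another rule supply the hold?**

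- The osimertinib text after the tables says "dosing will be interrupted, and supportive therapy administered as required in accordance with local practice/guidelines", but for events the clinician associates specifically with osimertinib.
- The ILD/pneumonitis text says "an interruption in study treatment dosing is recommended". This is one event type.
- Section 7 also bars restarting study treatment after QTc prolongation with signs of serious arrhythmia. This too is one event type.
- Section 6.4 lists reasons to stop therapy and gives no recovery grade.

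None is a general hold for telaglenastat.

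**3. How long could dosing continue?** This depends on which osimertinib rule the site applies.

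- *Table row taken literally:* osimertinib is held for a grade 3/4 event, and the cell sets no relatedness condition. If the event has not recovered and the delay passes 2 weeks, the footnote ends protocol therapy, so telaglenastat stops too. The limit is about 2 weeks per event.
- *Osimertinib text applied:* osimertinib is interrupted only for events associated with it. An event attributed to telaglenastat alone then triggers no delay, and the 2-week limit never starts.

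**4. Dose continued after a one-level reduction.** Section 6.1 gives "1) 400 mg PO BID; 2) 600 mg PO BID; 3) 800 mg PO BID", with 200 mg BID as Level −1.

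- From 800 mg BID, the expansion dose: 1,200 / 1,600 mg per day = 75%
- From 600 mg BID: 800 / 1,200 = 67%
- From 400 mg BID: 400 / 800 = 50%

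**5. Events covered.** The Section 10.1.1.1 table, "Adverse Events with Possible Relationship to Telaglenastat (CB-839) HCl (CTCAE 5.0 Term) [n= 161"], lists 11 terms: anemia, photophobia, nausea, vomiting, fatigue, ALT, alkaline phosphatase, AST, GGT, platelet count decreased and anorexia. Only ALT has its own Section 7 table, so 11 − 1 = 10 fall under other AEs. Fatigue, the only term in the above-20% column, is among them. This counts terms, not grade 3/4 events.

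**6. Remaining window.** From the version date (09/17/2024) to the end of telaglenastat therapy (2/28/25): 13 + 31 + 30 + 31 + 31 + 28 = 164 days, and 164 / 28 = 5.9 cycles. A further amendment would use up part of this.

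**The case against.** The strongest reply is that the rule is deliberate. Table and introductory text agree: interrupt for persistent grade 2, reduce for most related grade 3/4 events, and single out ALT and bilirubin for interruption. That agreement stands. A reader might infer a contradiction between text and table, and the documents do not support it. They also give no reason for leaving out the hold, and the delay footnote left on cells that order no delay, with the reduction cap missing, looks more like an omission.

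A reader might also infer that grade 2 is simply treated more strictly than grade 4. That goes too far. The grade 2 hold covers only persistent events and resumes at the same dose, whereas grade 3/4 brings a reduction. What remains is that the more severe event has no stated pause.

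A third tempting inference is dosing without limit through an unresolved event. The osimertinib cell in the same row may cap this at about 2 weeks, as shown above, so the exposure is bounded on one reading and open on the other.

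Finally, nothing shows that a site has dosed through such an event. Section 2.3 reports that the DLT patient's mucositis and pneumonitis resolved with supportive care and treatment withheld. Pneumonitis has its own rule, so this is only suggestive. Section 2.2.1.3.2 describes adverse events on the BID schedule as typically grade 1/2 and manageable without interruption. Both points lower the likely frequency; neither supplies the missing instruction.

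**Conclusion.** The point holds as a limited safety weakness that is cheap to correct. Two of 12 grade 3/4 cells lack a hold and a recovery grade, and no other section supplies a general one for telaglenastat. Taken literally, a patient on 800 mg BID would continue on 75% of the daily dose through a related grade 3 or 4 event, for about 2 weeks or longer depending on which osimertinib rule is applied.

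This assumes that sites follow the cell as written and do not hold on their own judgment. Reach is small: the summary of changes records accrual as permanently closed, so only patients still on telaglenastat up to 2/28/25 are affected. The documents do not give their number, or how many of the 10 terms can reach grade 4. A reader might infer that the RP2D, the DLT counts or the toxicity analysis are compromised. Nothing in the documents supports that.

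**What to change.** Change both telaglenastat cells (grade 3 and grade 4, other AEs) to:

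`If related to telaglenastat: Hold* until <= grade 1 or baseline, then resume one dose level lower.** Laboratory abnormalities not considered clinically significant by the PI do not require a hold.`

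The baseline alternative is needed because criterion 3.2.1 admits some patients with irreversible toxicity above grade 1, who could not otherwise meet the restart rule if that toxicity worsened. It and the laboratory exemption follow the approach of the DLT definition in Section 6.2. The double asterisk restores the cap on reductions.

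Align the general sentence in the introduction so that dosing is held and then reduced for most telaglenastat-related grade 3/4 toxicities. Unrelated events stay as they are. As an editorial matter only, change the ALT/bilirubin interruption threshold in that paragraph from above grade 2 to grade 2 or higher; both tables already hold at grade 2.

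Cost: two cells, one sentence and one inequality sign, with no added visits, samples or patients. The downside is somewhat more telaglenastat interruption, and some patients may reach the 2-week limit and go off therapy.
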